**Medtronic Confidential**

This document is electronically controlled

056-F275, v3.0 Clinical Investigation Plan Template

		Aortic and Tricuspid valves HF parameters (LVEF, LVEDD, LAD, etc.)
12 Month Follow Up (data reported up to day 395 (365 +/- 30 days) post procedure date will be collected)	Health Assessment	Subject Assessment (Cardiac rhythm, NYHA, etc.) Serious Adverse Events including major adverse cardiac or cerebrovascular events (MACCE) as defined in section 11.1 Medication
	Echo	MR Mitral Gradient Leaflet coaptation Aortic and Tricuspid valves HF parameters (LVEF, LVEDD, LAD, etc.)
	Study Exit	Exit

The following figure (Figure 3) is indicative of the study methods.

Figure 3: Study Methods

## 9.2. Subject Screening

Patients indicated for mitral repair procedure will be considered for enrollment in this study, and screened based on inclusion/exclusion criteria mentioned in Section 8. Site will maintain a Screening Log to maintain screening information.

## 9.3. Prior and Concomitant Medications

During the course of the study, subjects will continue to take medication as advised by their physician per standard of care. The study does not advise or limit the subject from any particular medication.

## 9.4. Subject Consent

The investigator or authorized designee must obtain written informed consent before any study related activity takes place.

Prior to the consent discussion, the patient should receive the EC/IRB approved Patient Information and Patient Informed Consent Form. During the consent discussion the investigator or his/her authorized designee must fully inform the patient of all aspects of the study that are relevant to the patient's decision to participate in the study. If a patient is illiterate, an impartial witness must be present during the entire informed consent discussion. All items addressed in the Patient Information and the Patient Informed Consent Form must be explained. The language used shall be as non-technical as possible and must be understandable to the patient and the impartial witness, where applicable.

The patient must have ample time and opportunity to read and understand the Patient Information and the Patient Informed Consent Form, to inquire about details of the study, and to decide whether or not to participate in the study. All questions about the study should be answered to the satisfaction of the patient.

Neither the investigator, nor the investigation site staff shall coerce or unduly influence a patient to participate or to continue to participate in the study. The informed consent process shall not waive or appear to waive the patient's rights.

When the patient decides to participate in the study, the Patient Informed Consent Form must be signed and personally dated by the patient and investigator or authorized designee. If applicable, the witness shall also sign and personally date the consent form to attest that the information in the Patient Information and Patient Informed Consent Form was accurately explained and clearly understood by the patient, and that informed consent was freely given.

After all persons have signed and dated the Patient Informed Consent Form, the investigator must provide the patient with a copy of the Patient Information and the signed and dated Patient Informed Consent Form.

This study does not require any additional interventions other than the standard of care, and hence, the subject will be treated as per physician's discretion in case of requirement of emergency treatments.

It will be the investigator's responsibility to fulfil any additional EC requirements, if any on the informed consent process.

## 9.5. Randomization and Treatment Assignment

PRESERVE-Mitral is a prospective non-randomized non-interventional post-market registry and does not involve randomization.

## 9.6. Medication Compliance

The study will not be prescribing any particular medication, all subjects will continue on their medication as prescribed by their physicians per standard practice.

## 9.7. Assessment of Efficacy

This is a post-market registry assessing long term clinical outcomes.

## 9.8. Assessment of Safety

Serious Adverse Events and Device Deficiencies throughout the study will be collected and recorded in the AE and DD CRF's. All Adverse Events and Device Deficiencies will be reviewed by Medtronic Safety Representative. Safety Representative will ensure the timely review and reporting of all events. Safety assessment will be documented in the safety database. The types of events and reporting requirements are described in section 11 below.

### **Product Complaint:**

Any written, electronic or oral communication that alleges deficiencies related to the identity, quality, durability, reliability, safety, effectiveness or performance of a medical device that has been released for distribution. Any complaint involving the possible failure of a device, labeling or packaging to meet any of its specifications is subject to reporting. Devices/products used in this study are commercially available in the countries participating in the study. Product complaints are not within the scope of this CIP and should be reported in addition to the Adverse Event reporting requirements. It is the responsibility of the investigator to report all product complaint(s) associated with a medical device distributed by Medtronic, regardless whether they are related to intended use, misuse or abuse of the product, promptly.

## 9.9. Recording Data

The following table (Table 4) lists out the data collection requirements for each visit related to the study.

**Table 4. Data Collection Requirements**

	Baseline / Pre-Operative (data from most recent assessment from planned implant date preferred, not exceeding 60 days)	Implant	Discharge (date of discharge or 7 days post procedure, whichever comes first)	3-6 month Follow Up (data reported from 90 days up to 210 days post procedure, whichever comes later)	12 month Follow Up (data reported up to day 395 (365 +/- 30 days) post procedure date will be collected)
Inclusion/Exclusion Criteria	X				
PIC	X				
Patient demographics	X				
Pre-operative clinical history	X				

**Medtronic Confidential**

	Baseline / Pre-Operative (data from most recent assessment from planned implant date preferred, not exceeding 60 days)	Implant	Discharge (date of discharge or 7 days post procedure, whichever comes first)	3-6 month Follow Up (data reported from 90 days up to 210 days post procedure, whichever comes later)	12 month Follow Up (data reported up to day 395 (365 +/- 30 days) post procedure date will be collected)
Mitral Valvular Lesion and Risk Factors	X				
Cardiac Rhythm Assessment	X		X	X	X
Heart Failure Symptoms	X		X	X	X
NYHA Classification	X		X	X	X
Medications	X		X	X	X
Echocardiography including MR grade, mitral gradient, coaptation, LVEF, LVEDD, LAD and tricuspid and aortic valve assessments	X	X 	X	X	X
Implant Details		X			
Concomitant Procedures		X			
Re-operation			X	X	X
Serious Adverse Events including MACCE (as defined in section 11.1)		X	X	X	X
Device Deficiency		X	X	X	X
Death			As they occur		
Protocol Deviation			As they occur		
Study Exit					X

(1) TEE specific parameters will be collected for TEE done at implant

### 9.9.1. Enrollment (Baseline) Visit

Besides the PIC and the meeting of the in/exclusion criteria, the following information will be collected:

- Demographics such as age and gender will be collected after enrolling subject
- Medical History such as etiology and history of previous surgical intervention will be documented
- Cardiac rhythm will be documented, measured as per standard practice (ECG/Holter)
- Heart failure symptoms (such as dyspnea, persistent coughing, edema, fatigue, nausea, orthopnea, confusion, increased heart rate) will be collected and results of physical examination (such as systolic and diastolic blood pressure, NYHA class) will be documented
- Evaluation of the mitral valvular lesion will be done and documented (Rheumatic, Ischemic, etc)
- Medication – The drug therapy provided to the subject at the enrollment visit will be documented

- Echocardiography – Transthoracic echo (TTE) data will be collected, documenting mitral valve regurgitation grade, mitral gradient and coaptation, right/left atrial, ventricular size and functional information (including aortic and tricuspid evaluation), etc.

Data from the most recent assessment before the planned implant date will be preferred, not exceeding 60 days.

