# PRESERVE-Mitral Clinical Investigation Plan

MDT16016SUR002

Version 1.0, dated 10-APR-2017

Page 10 of 58

Medtronic

	and procedural outcomes of the procedure.
Study Design	PRESERVE-Mitral Registry is a prospective non-randomized, non-interventional, post-market registry.
Sample Size	200
Inclusion/Exclusion Criteria	
Inclusion Criteria:
 

1. Patients with valvular insufficiency and/or stenosis and indicated for the reconstruction and/or remodeling of pathological mitral valves with Profile 3D™ and CG Future® annuloplasty systems

2. Indications and contraindications provided in the product Instructions for Use

3. Subject is 18 years of age or older

4. The patient or his/her Legally Authorized Representative (LAR) has been informed about the nature of the registry and the patient informed consent for study participation has been obtained prior to performing any study-related procedures from the subject or Legally Authorized Representative, as per applicable local requirements

 
Exclusion Criteria:
 

1. Contraindications as per IFU:

a. Heavily calcified valves

b. Valvular retraction with severely reduced mobility

c. Active bacterial endocarditis

2. Aortic valve replacement as concomitant procedure

3. Already participating in another clinical study, possibly leading to bias and jeopardizing the scientific appropriate assessment of the study endpoints

Study Procedures and Assessments	

• Baseline/Pre-Operative (data from most recent assessment before planned implant date preferred, not exceeding 60 days)

• Implant

• Discharge (date of discharge or 7 days post procedure, whichever comes first)

• 3 to 6 months (data reported from 90 days up to 210 days post procedure, whichever comes later)

• 12 months (data reported up to day 395 (365 +/- 30 days) post procedure date will be collected)

Safety Assessments	All relevant safety data will be collected and reported per local regulations and EC/IRB requirements

---

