Stroke is defined as an acute episode of focal or global neurological dysfunction caused by brain, spinal cord, or retinal vascular injury as a result of hemorrhage or infarction, where the neurological dysfunction lasts for greater than 24 hours. The occurrence of stroke will be evaluated at 6 months and 12 months post procedure.

- New onset of Atrial Fibrillation, as evaluated through follow up ECG at discharge, first follow up (3-6 months) and at second follow up (12 months)

New onset of AF is defined as when the subject did not present with prior history of AF at baseline nor was AF detected at baseline visit, but AF did manifest post procedure and was either diagnosed during the study visits (discharge, 3-6 months or 12 months visit) or was otherwise diagnosed during the duration of subject participation in the study. The incidence of new onset AF will be evaluated at discharge, first follow up (3-6 months) and at second follow up (12 months).

- Number of attempts required for procedural success, and bypass time as a measure of procedural complexity, as measured by standard operating room procedures at the site.

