#### 7.1.3 Analysis Sets

There are three analysis sets defined for this study. Analysis sets used for each objective are defined in the corresponding objective section. The primary analysis set is the Successfully Implanted analysis set.

- Enrolled analysis set: Composed of all subjects who signed the Patient Informed Consent Form. Time zero begins on the date of informed consent.
- Attempted Implant analysis set (AT): Composed of all enrolled subjects who were attempted for a Profile 3D™ or CG Future® Annuloplasty system implantation. A subject with one or more attempts of the Medtronic study device recorded on the procedure case report form (CRF) is considered as implant attempted. Time zero begins on the date of the first attempted procedure.
- Successfully Implanted analysis set (IMP): Composed of all AT subjects who had either a Profile 3D™ or CG Future® Annuloplasty system implanted successfully. Time zero begins on the date of implant procedure.

All data collected from enrolled, attempted implant, and successfully implanted subjects will be utilized in the analyses as appropriate. Analyses of the primary and secondary endpoints will be descriptive, and no statistical hypothesis tests will be performed.

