**7.9.9 Secondary Endpoint #7**

New onset of atrial fibrillation (AF), as evaluated through follow up ECG at discharge, first follow up (3-6 months) and at second follow up (12 months), as well as on the AE form.

Hypothesis/Decision criteria:

No specific hypotheses or pass/fail criteria have been set. The analysis will be descriptive and no statistical hypothesis test will be performed.

Endpoint Definition/Parameters to Be Estimated:

New onset of AF is defined as when the subject did not present with prior history of AF at baseline nor was AF detected at baseline visit, but AF did manifest post procedure and was either diagnosed during the study visits (discharge, 3-6 months or 12 months visit) or was otherwise diagnosed during the duration of subject participation in the study.

Data Collection and Analysis Dataset:

Data will be collected on a DISCHARGE/FOLLOW UP (SV) CRF or an AE CRF.

This objective will be analyzed for the Successfully Implanted (IMP) cohort.

Analysis Method:

A Kaplan-Meier analysis will be performed.

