## **7.12 Changes to Planned Analysis**

Analysis set defined in the CIP for the primary and secondary endpoints is changed to the Successfully Implanted set in order to align with other surgical valve studies.

New onset of atrial fibrillation will be evaluated using Kaplan-Meier method instead of percent of subjects as described in the CIP in order to incorporate subject censoring in the course of the study. Atrial fibrillation identified on the post-procedural ECG or AE forms will be included in the analysis.

Changes to V1.0 of the SAP include: Baseline data will be presented for the Enrolled and Successfully Implanted cohorts, and procedural data will be presented for the Attempted Implant and Successfully Implanted cohorts. As one of the objectives of the registry is to characterize subjects who are considered eligible for mitral valve repair in South Asia, analyzing baseline and procedural characteristics on these analysis cohorts will cover the populations of interest.

Sub-group analyses will be performed on the Successfully Implanted subjects with CG Future Band, CG Future Ring and Profile 3D Ring respectively for the primary and selected secondary endpoints.

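### New-onset AF is judged against a rhythm reading up to 60 days old with none required at implant, so AF starting between that reading and surgery can count as new onset

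*Combined protocol and SAP*

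**What the plan says.** **Baseline window.** CIP 9.9.1 says of the baseline visit: "Data from the most recent assessment before the planned implant date will be preferred, not exceeding 60 days". The synopsis has the same rule ("data from most recent assessment before planned implant date preferred, not exceeding 60 days"), and the Schedule of Events and Table 4 also refer to the planned implant date and 60 days.

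**Rhythm records.** In CIP Table 4 the row "Cardiac Rhythm Assessment" is marked at baseline, discharge, 3-6 months and 12 months. The implant column is blank. CIP 9.9.2, which lists the implant data, has no rhythm item.

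**Definition.** CIP 5.2.2 counts AF as new onset under this condition: "the subject did not present with prior history of AF at baseline nor was AF detected at baseline visit, but AF did manifest post procedure". SAP 7.9.9 repeats the exclusion ("did not present with prior history of AF at baseline nor was AF detected at baseline visit"). SAP 7.12 adds: "Atrial fibrillation identified on the post-procedural ECG or AE forms will be included in the analysis".

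**Clock.** For the Successfully Implanted set, on which this endpoint is analysed, SAP 7.1.3 says: "Time zero begins on the date of implant procedure". SAP 7.9.9 prescribes a Kaplan-Meier analysis.

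**The concern.** The endpoint is meant to describe AF that arises after the repair. To do so it needs to know that the subject was free of AF when the operation began. The plan establishes freedom from AF at the baseline assessment instead, and no required data item covers the time between that assessment and surgery. A subject who goes into AF in that interval and is in AF on the discharge ECG meets every element of the new-onset definition.

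This is a stated rule that misplaces certain cases, always in the same direction. The registry has a single arm, so no comparator carries the same error and cancels it. The reported confidence interval would not reflect it. If the last preoperative rhythm is not collected prospectively, it may not be recoverable at analysis.

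**Working it through.** **Step 1. Follow one subject through the rules.** The documents give no figure for this point, so the first check is textual. Take a subject with no AF history and sinus rhythm at the baseline assessment, who goes into AF before surgery and is still in AF at discharge.

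- History at baseline: negative, so not excluded.
- Rhythm at baseline: no AF, so not excluded.
- Implant: no rhythm field in Table 4 or 9.9.2. Serious adverse events are also marked in Table 4 only from implant onward, so that route does not capture the onset either.
- Discharge: AF on the post-procedural ECG, so an event under SAP 7.12.
- Date: for partial dates, SAP 7.4 does not let a resolved date fall before the procedure, so a resolved date cannot show the preoperative start.

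The subject is scored as new onset. An event found by day 7 would already be in the earliest Kaplan-Meier estimate, since SAP 7.2 places the discharge estimate at 7 days.

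**Step 2. Who is affected.** Subjects with known AF or AF at the baseline reading are already excluded. Only AF that begins after that reading, or is missed at it, and then appears postoperatively is misclassified. This does not depend on a postponed operation: surgery on the planned date still leaves a permitted gap of up to 60 days. Postponement can only lengthen it.

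**Step 3. Size, on assumed inputs.** The documents give no AF onset rate, no share of subjects free of AF and no distribution of the gap. Assumptions:

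- onset rate r before surgery: 5%, 10% or 15% a year
- 120 of the 200 subjects AF-free at baseline
- true 12-month new-onset risk t = 10% (30% as a sensitivity)
- every subject has the full gap of d days, and all AF starting in the gap is seen after surgery

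Formulas: share with onset in the gap, g = 1 - exp(-r × d/365). Apparent risk = g + (1 - g) × t. Excess = g × (1 - t). Relative excess = g × (1 - t)/t.

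Worked case, r = 15%, d = 60: g = 1 - exp(-0.15 × 60/365) = 2.44%. Misclassified subjects = 120 × 0.0244 = 2.9. Apparent risk = 0.0244 + 0.9756 × 0.10 = 12.2%. Excess = 2.2 points, or 21.9% relative.

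| Gap (all subjects) | g, for r = 5-15% | Misclassified of 120 | Excess, t = 10% | Relative, t = 10% | Relative, t = 30% |
|---|---|---|---|---|---|
| 30 days | 0.4-1.2% | 0.5-1.5 | 0.4-1.1 points | 4-11% | 1.0-2.9% |
| 60 days | 0.8-2.4% | 1.0-2.9 | 0.7-2.2 points | 7-22% | 1.9-5.7% |
| 120 days | 1.6-4.8% | 2.0-5.8 | 1.5-4.3 points | 15-43% | 3.8-11.2% |

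The net excess in subjects is slightly below the misclassified count, because a fraction t of them would have been counted anyway: at 60 days and t = 10%, 0.9-2.6 subjects. The 120-day row would need every subject to have a baseline at the limit plus a 60-day postponement.

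**Step 4. Set against sampling error.** As a rough yardstick, the exact binomial 95% interval for 12 of 120 (10%) is 5.3% to 16.8%. The 60-day excess of 0.7-2.2 points lies well inside that.

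**The case against.** The best case against acting is that the effect is small and hypothetical. Sixty days is an outer limit, the text prefers the most recent assessment, and many baseline readings may be taken close to surgery. All inputs to the size are assumed, the table applies the longest gap to everyone, and the excess is smaller than the sampling error of a secondary endpoint in a descriptive registry with no pass/fail criteria. All of this stands, and it is why the figures are upper bounds for the stated assumptions. It does not remove the point: the misclassification follows from the definition as written, has a known direction, and is cheap to prevent.

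A reader might infer three stronger things that the documents do not support.

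- *All AF that began before the operation is counted as new onset.* It is not. Known history and AF at the baseline visit are excluded.
- *Tying the window to the planned date is the cause.* The gap exists when surgery is on time, so changing planned to actual would not close it. Nor does the text say that the window stays with the first planned date; a rescheduled operation may simply have a new one. The documents do not settle this, and they are also unclear whether a preference makes 60 days a hard limit.
- *Postponed patients have outdated NYHA and MR baselines that bias those results.* An older baseline is possible, but neither a direction nor a size for NYHA or MR follows from the documents.

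**Conclusion.** The point holds for new-onset AF. AF that starts after the baseline assessment, or is missed at it, but before surgery, and is seen afterwards, is counted as new onset, which biases secondary endpoint #7 upward. With 5-15% onset a year, 120 AF-free subjects, a 10% true rate and a full 60-day gap for all, the upper bound is about 1-3 misclassified subjects, 0.7-2.2 points or 7-22% relative. It is less for shorter gaps or a higher true rate, and reaches 15-43% relative only if every subject had a 120-day gap. The relative figures depend heavily on the assumed 10%. The planned-date wording is a minor ambiguity. No primary endpoint is shown to be affected. This is a low-cost improvement to a named endpoint and does not threaten the registry's main results.

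**What to change.** 1. Add one field (with its date) to the implant eCRF and to Table 4 and CIP 9.9.2: the last documented rhythm before incision, transcribed from existing records where available. No test is added, which fits the standard-of-care design in CIP 6.2.
2. In SAP 7.9.9, state that AF present at that record is baseline AF and not new onset. Where no such record exists, fall back on the baseline assessment and report how many subjects this concerns.
3. As a minor clarification in the synopsis, Schedule of Events, Table 4 and CIP 9.9.1, state the 60-day window relative to the actual implant date, take the last assessment before surgery as baseline, and say whether 60 days is a limit or a preference. Report the distribution of the baseline-to-implant interval.

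Cost: one transcribed field, one or two sentences in the SAP, wording in four places of the CIP, and slightly fewer subjects at risk for new-onset AF. A single preoperative record can still miss intermittent AF, so the change reduces the misclassification without fully removing it.

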## 9.9.2. Implant Visit

The implant will be performed as per surgeon's discretion and standard practice. The following information will be collected during the implant procedure.

- Details of surgical approach and procedural complexity (cross-clamp time, concomitant procedures, etc) will be documented
- Mitral valve pathology (valve dilatation, calcification, prolapse, etc) and leaflet segments affected (A1, A2, A3, P1, P2, P3) will be documented
- Details of mitral repair along with the ring/band annuloplasty (papillary muscle repair, chordal replacement or shortening, etc) and sizing of mitral valve annulus will be documented
- Serious Adverse Events including MACCE (as defined in section 11.1) during the implant will be documented, and an Adverse Event form will also be filled out
- Echocardiography – Transoesophageal echo (TEE) data will be collected, documenting various TEE parameters routinely evaluated during annuloplasty procedure.

